6.5.5 Management of Specific Adverse Events or Adverse Drug Reactions

No specific measures are proposed at this stage. Standard medical care will be provided at the trial site for all AEs occurring during the trial.

6.6 Packaging and Labeling of the Investigational Medicinal Product

All IMPs will be packaged and labeled in accordance with all applicable regulatory requirements and Good Manufacturing Practice Guidelines.

M2951 and matching placebo is supplied by the Sponsor. A description of the pharmaceutical properties and composition of the formulation of M2951 is provided in the IB. Additional details of packaging and labeling of the IMP will be defined in a separate Operations Manual.

6.7 Preparation, Handling, and Storage of the Investigational Medicinal Product

Because the Investigator is blinded to trial treatment, subjects will be instructed on the proper handling and storage of the IMP by the trial nurse or pharmacist. Storage at or below 25°C is recommended.

Any unused product should be returned to the trial site.

6.8 Investigational Medicinal Product Accountability

The Investigator or designee is responsible for ensuring IMP accountability, including reconciliation of drugs and maintenance of records.

- Upon receipt of the IMP, the responsible person will check for accurate delivery and acknowledge receipt by signing or initialing and dating the appropriate documentation and returning it to the location specified. A copy will be archived for the Investigator Site File.
- IMP dispensing will be recorded on the appropriate drug accountability forms so accurate records will be available for verification at each monitoring visit.
- Trial site IMP accountability records will include the following:
 - Confirmation of IMP receipt, in good condition and in the defined temperature range
 - The inventory of IMP provided for the clinical trial and prepared at the site
 - The use of each dose by each subject
 - The disposition (including return, if applicable) of any unused IMP
 - Dates, quantities, batch numbers, expiry dates, and the individual subject trial numbers.

The Investigator site should maintain records, which adequately document the subjects were provided the doses specified in this protocol, and all IMPs provided were fully reconciled.

Unused IMP must not be discarded or used for any purpose other than the present trial. No IMP dispensed to a subject may be redispatched to a different subject.

A Trial Monitor will periodically collect the IMP accountability forms.

6.9 Assessment of Investigational Medicinal Product Compliance

The IMP will be administered at the site on trial visit days as defined in [Table 1](#). All other dosing will be done by the subject at home throughout the rest of the trial. Subjects will be asked to record the date and time of dosing and food intake around dosing in a subject diary. Diaries will be collected and reviewed at the trial visits specified in [Table 1](#).

Subjects will be instructed to bring all IMP, including the used packaging, to each trial visit to allow for the assessment of compliance with trial treatment. Prior to discharge from each scheduled visit, subjects will be given sufficient IMP for at-home dosing until the next scheduled visit during the treatment period.

6.10 Blinding

This will be a double-blind trial. After Day 1, the study site staff, the Sponsor, and the [PPD](#) study team will be blinded to:

- Results that can reveal the PD effects of M2951 in an individual subject (ie, immunoglobulins [IgA, IgM, IgG, and its subclasses], [CCI](#) [REDACTED], and B cell numbers and subtypes) and
- Results that can reveal the efficacy of M2951 in an individual subject (ie, hsCRP, ESR, anti-CCP, and RF).

Blinding to treatment codes or laboratory results capable of revealing treatment will be maintained throughout the trial duration, except for the unblinded IDMC, limited unblinding for the purposes

of the IA, partial unblinding to support early analysis of PK/PD data, or in the event that emergency unblinding is necessary (see Section 6.11). The blind may also be broken in the case of a pregnancy should the subject desire this information. Randomization data will be kept strictly confidential, accessible only to authorized staff, until the limited unblinding for the IA and full unblinding for the analysis at the end of 12 weeks of treatment for all randomized patients.

In order to maintain the blinded nature of the study, only the randomization statistician, an independent person at the study site responsible for receiving local laboratory ESR results and conveying those results to the central laboratory, and an independent statistician team (independent of the PPD study team) responsible for production of the IA outputs, will be fully unblinded during study conduct. The bioanalytical laboratory(ies) responsible for the analysis of the PK and PD samples will be allowed to be partially unblinded during study conduct using masked subject identifiers, to support association of PK/PD data with treatment codes for timely decision making, but prevent association of treatment codes with any other clinical data, such as safety data. A subteam of the Sponsor study team tasked with review of the IA data (medical responsible, Drug Safety representative, and biostatistician) will be unblinded to the IA results, which will be presented in the form of summary tables on a limited set of endpoints for subjects enrolled at the time of the IA: 4-week hsCRP, 4-week DAS28-hsCRP, safety, baseline characteristics, and disposition. The IDMC will also be unblinded to treatment, as described in the IDMC charter.

All other trial-related individuals, ancillary site staff, other clinical research associates/monitors, investigators, Sponsor staff other than those identified above, and PPD staff other than those identified above, will remain blinded to treatment codes or laboratory results capable of revealing treatment. Results from PK and PD testing or the IA will not be reported back to the sites or the PPD study team, with the exception of ESR results. The ESR results will be analyzed at a laboratory local to the site, received by a person at the site independent of study staff at the site, and conveyed to the central laboratory without sharing with study staff at the study site, the Sponsor, or the PPD study team. There will be no communication of results between the PPD study team tasked with conduct of the study and the independent statistician team responsible for the production of IA outputs.

Only when the 12-week Treatment Period is completed for all patients, the data file verified, protocol violations determined, statistical analysis plan (SAP) signed and database partially locked for the 12-week treatment period, will the drug codes be broken and made available, along with laboratory results capable of revealing treatment, for the primary data analysis. The final analysis will be performed after all subjects have completed the Safety Follow-up or discontinued from study early, with assessment of some safety and key efficacy variables.

All breaks of the trial blind must be adequately documented.

Processes to maintain blinding during the IA are described in Section 8.6.

6.11 Emergency Unblinding

There is no known antidote to M2951, so symptomatic and supportive treatment of any suspected and related AE, if necessary, is to be undertaken as clinically indicated.

The trial blind may be broken for an individual only if knowledge of the IMP is essential for clinical management of the subject. Contact information for breaking the blind in an emergency is given on the subject emergency card provided to each subject (see Section 9.4).

The Investigator will have the ability to break the blind with regard to IMP for any subject through the IWRS. However, the Investigator should make every effort to contact the responsible Medical Monitor or their designee to discuss the subject's emergency situation and the need to unblind prior to unblinding any subject. The Investigator must contact the Sponsor or designee within 1 working day after the event occurs without revealing to the Sponsor personnel the result of the code break. The Investigator will be able to access the subject's treatment assignment 24 hours a day through the IWRS using a unique access code and user number (different from those used to assign subjects to treatment through the IWRS). The Investigator must record the date and reason for unblinding in the subject's eCRF and source documents.

Under certain circumstances, Drug Safety may be required to unblind the treatment assignment for an individual subject following an SAE or other serious event, eg, if an expedited regulatory report is required. See Section 7.4.1.4 for further details on expedited reporting and SAEs.

If emergency unblinding is required, discontinuation of the affected subject from the IMP and/or trial is not mandatory unless there are other circumstances that require subject discontinuation. If the affected subject is discontinued from the IMP, the subject must immediately complete the End of Treatment Visit, followed 4 weeks later by the Safety Follow-Up/End of Trial Visit.

6.12 Treatment of Overdose

For purposes of this protocol, an overdose is defined as any dose greater than twice the highest daily dose included in the clinical trial protocol or planned for an individual subject enrolled in the trial, administered on 3 or more consecutive days. Even if it does not meet other criteria for an SAE, any overdose must be recorded in the trial medication section and AE section of the eCRF and reported to Drug Safety in an expedited manner using the paper SAE Report Form, and following the same timelines in Section 7.4.

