6.13 Medical Care of Subjects after End of Trial

After a subject has completed the trial or has withdrawn early, the subject is free to access further treatment as deemed appropriate by the treating physician.

7 Trial Procedures and Assessments

During the Screening Visit, prior to performing any trial assessments that are not part of routine medical care for the subject, the Investigator will obtain written informed consent as described in Section 9.2.

Throughout the trial, subjects will undergo the assessments detailed in Table 1, including blood sampling. The maximum amount of blood to be obtained during the trial is within the commonly accepted maximum of 275 mL over 4 weeks and 550 mL over 8 weeks. Details of the blood volumes to be collected for each sample/visit will be detailed in the Laboratory Manual.

Instructions on how samples will be collected, labeled, processed, stored, and shipped as well as specification on bioanalytical methods will be detailed in the Laboratory Manual.

All blood and urine tests will be analyzed by a central laboratory, with the following exceptions:

- Urine testing for beta-human chorionic gonadotropin (β -HCG) will be conducted at the local laboratories
- PK samples and CCI [REDACTED] samples will be analyzed by the analytical laboratories specified by the Sponsor
- Blood samples will be sent for duplicate analysis of selected safety tests by both central and local laboratories. These duplicate safety samples are listed in the Laboratory Manual.
- ESR will be analyzed by local laboratories

Every effort should be made to perform assessments as close as possible to the scheduled time points, within the range of days noted for each day on trial as noted in [Table 1](#). The details of efficacy assessments and safety assessments are described in Sections [7.3](#) and [7.4](#), respectively.

The Schedule of Assessments for the trial is presented in [Table 1](#) and details of the trial procedures are provided in Section [7.1.1](#) for the Screening Period, Section [7.1.2](#) for the Treatment Period, and Section [7.1.4](#) for the Follow-Up Period.

The Sponsor and CRO should be notified immediately of any major violations of the trial procedures. Major and minor protocol violations will be defined in the Manual of Procedures (MOP) and in the SAP. Procedures for documenting protocol violations will be provided in the MOP.

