7.4.1.2 Methods of Recording and Assessing Adverse Events

At each trial visit, the subject will be queried on changes in his or her condition. During the reporting period, any unfavorable changes in the subject’s condition will be recorded as AEs, whether reported by the subject or observed by the Investigator.

Complete, accurate, and consistent data on all AEs experienced for the duration of the reporting period (defined below) will be reported on an ongoing basis in the appropriate section of the eCRF. All SAEs must be additionally documented and reported using the appropriate Report Form as described in Section [7.4.1.4](#).

It is important that each AE report include a description of the event, its duration (onset and resolution dates (and times when it is important to assess the time of AE onset relative to the

recorded treatment administration time), its severity, its causal relationship with the trial treatment, any other potential causal factors, any treatment given or other action taken, including dose modification or discontinuation of the IMP, and its outcome. In addition, serious cases should be identified and the appropriate seriousness criteria documented.

Specific guidance can be found in the eCRF Completion and Monitoring Conventions provided by the Sponsor.

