7.4.1.4 Procedure for Reporting Serious Adverse Events

Serious Adverse Events

In the event of any new SAE occurring during the reporting period, the Investigator must immediately (within a maximum of 24 hours after becoming aware of the event) inform the Sponsor or its designee using the SAE Report Form following specific completion instructions.

In exceptional circumstances, an SAE (or follow-up information) may be reported by telephone; in these cases, the eCRF must be completed.

Relevant pages from the eCRF may be provided in parallel (eg, medical history, concomitant drugs). Additional documents may be provided by the Investigator, if available (eg, laboratory results, hospital report, autopsy report). In all cases, the information provided on the SAE Report Form must be consistent with the data about the event recorded in the eCRF.

The Investigator must respond to any request for follow-up information (eg, additional information, outcome, final evaluation, other records where needed) or to any question the Sponsor/designee may have on the AE within the same timelines as those noted above for initial reports. This is necessary to ensure prompt assessment of the event by the Sponsor or designee and (as applicable) to allow the Sponsor to meet strict regulatory timelines associated with expedited safety reporting obligations.

Requests for follow-up will usually be made via the responsible Medical Monitor, although in exceptional circumstances, the Global Drug Safety department may contact the Investigator directly to obtain further information or to discuss the event.

7.4.1.5

Safety Reporting to Health Authorities, Independent Ethics Committees/ Institutional Review Boards, and Investigators

The Sponsor will send appropriate safety notifications to Health Authorities in accordance with applicable laws and regulations.

The Investigator must comply with any applicable site-specific requirements related to the reporting of SAEs (particularly deaths) involving trial subjects to the IEC/IRB that approved the trial.

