10.1 Definition of Protocol Deviations and Analysis Sets

No per Protocol analysis is planned.

Important protocol deviations are protocol deviations that might significantly affect the completeness, accuracy, and/or reliability of the study data or that might significantly affect a subject's rights, safety, or well-being.

The following important deviations will be identified and confirmed prior to or at the Data Review Meeting, which will occur before the database lock. The outcome of the Data Review Meeting will document the important protocol deviations as well as the finalization of the analysis population in a memo.

- Subjects that are dosed on the study despite not satisfying the inclusion criteria
- Subjects that develop withdrawal criteria whilst on the study but are not withdrawn
- Subjects that receive the wrong treatment or an incorrect dose
- Subjects that receive an excluded concomitant medication
- Deviation from Good Clinical Practice

- Inclusion and exclusion criteria violations
- Other violations/events that may have a relevant influence on the pharmacokinetic/pharmacodynamic (PK/PD) analysis (eg, adverse events (AEs), vomiting, sample processing errors, inaccurate dosing, etc.)

Any important protocol deviations that lead to the exclusion of a subject from an analysis set will be considered clinically important (see [Section 10.2](#)).

All important protocol deviations should be documented in Clinical Data Interchange Standards Consortium Study Data Tabulation Model (SDTM) (or Analysis Data Model (ADaM) for those derived by programming) whether identified through sites monitoring, medical review and/or programming based on the inclusion/exclusion criteria presented in the protocol. Important protocol deviations to be identified by programming as well as all clinically important protocol deviations are listed and described in [Appendix 3](#).

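### Protocol 6.12 counts an overdose only after three consecutive days, so a one- or two-day overdose of any size without an SAE needs no overdose entry and no expedited report to Drug Safety

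*Protocol*

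**What the plan says.** Protocol Section 6.12 sets two joint conditions for an overdose. The dose must exceed twice the highest daily dose in the protocol "or planned for an individual subject enrolled in the trial, administered on 3 or more consecutive days". For an event that meets the definition, "any overdose must be recorded in the trial medication section and AE section of the eCRF", and it must go to Drug Safety on the paper SAE form under the SAE timelines. Section 7.4.1.4 gives that clock: "within a maximum of 24 hours after becoming aware of the event". Section 6.12 says these duties hold even where no other SAE criterion is met. Neither the protocol nor the SAP contains another overdose definition or reporting rule.

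Other provisions touch on excess intake:

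- **Diary (Protocol 6.9):** "Subjects will be asked to record the date and time of dosing and food intake around dosing in a subject diary". Table 1, footnote u, adds pill counts by visit interval, and Section 6.8 requires accountability records for each dose.
- **Adverse events (Protocol 7.4.1.2):** any unfavorable change in the subject's "condition will be recorded as AEs, whether reported by the subject or observed by the Investigator".
- **Violations (Protocol 7):** "The Sponsor and CRO should be notified immediately of any major violations of the trial procedures".
- **Deviations (SAP 10.1):** the list of important deviations includes "Subjects that receive the wrong treatment or an incorrect dose". These "will be identified and confirmed prior to or at the Data Review Meeting, which will occur before the database lock".
- **Programmed and reviewed checks (SAP Appendix 3):** PDEV38 flags compliance below 80% or above 120%. PDEV39 covers product not taken as the protocol directs, and its importance is decided case by case.

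**The concern.** By requiring an overdose to be expedited without waiting for an SAE, the protocol accepts that excess intake should reach Drug Safety before harm is shown. The three-day condition defeats that purpose for acute ingestion. It also puts cases in the wrong order: a smaller total spread over three days is expedited, while a larger total taken in one day is not. A site that knows of an acute overdose with no symptoms, or with only a non-serious AE, has no duty under 6.12 to tell Drug Safety. The information may arrive late or not at all.

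This is a Phase IIa trial of an irreversible inhibitor. Section 6.11 says there is no known antidote, and Section 3.1 lists hemorrhage, cytopenias, hepatocellular injury and atrial fibrillation among the potential risks. Section 3.1 also relies on an IDMC that reviews safety data continually, which depends on prompt capture.

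**Working it through.** The plan gives no figure of its own to reproduce. The check is dose arithmetic followed by a comparison of reporting routes.

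**Inputs**
- Planned dose: 2 capsules of 25 mg twice daily for 84 days (Protocol 6.2); tablets of the same strength and number in the extension (Protocol 6.1 and 6.2).
- Kit size: 36 capsules (SAP 15).
- Last on-treatment interval: Day 57 to Day 85, 28 days (Protocol Table 1).
- Compliance: capsules taken divided by capsules due, times 100 (SAP 15).

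**Threshold**
- Daily dose: 2 × 25 × 2 = 100 mg, or 4 capsules.
- Limit: 2 × 100 = 200 mg, or 8 capsules. The first whole-capsule intake above it is 9 × 25 = 225 mg.

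**Reportable and non-reportable intakes**

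| Intake | Total | Meets the 6.12 definition? |
|---|---|---|
| 9 capsules a day for 3 days | 27 × 25 = 675 mg | Yes |
| 36 capsules over 2 days (18 a day, 450 mg a day) | 900 mg | No, 2 days |
| 36 capsules in 1 day | 36 × 25 = 900 mg | No, 1 day |

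The one-day kit is 900/100 = 9 times the daily dose and 900/675 = 1.33 times the smallest reportable total. The supply is realistic: between Day 57 and Day 85 a subject needs 28 × 4 = 112 capsules.

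**Would the compliance check catch it?** Take one kit in one day and normal dosing otherwise.
- By interval, Day 57 to Day 85: (36 + 27 × 4)/(28 × 4) = 144/112 = 128.6%. This is above 120% and would be flagged.
- Over 84 days: 84 × 4 = 336 capsules due and 36 − 4 = 32 extra, so 368/336 = 109.5%. This would not be flagged.

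The SAP does not say which period PDEV38 uses. Section 15 tabulates 12-week compliance only from first to last intake, which favors the second figure. Either way, PDEV38 is a deviation check and sends nothing to Drug Safety.

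**Would another route give a prompt report?**
- SAE reporting is prompt but needs a seriousness criterion to be met.
- AE recording needs an unfavorable change in condition. It goes to the eCRF and is not expedited.
- The incorrect-dose deviation need only be confirmed by the Data Review Meeting before database lock.
- The immediate notice in Protocol 7 covers major violations and goes to the Sponsor and CRO. The SAP classifies deviations as important, not major, and never links either term to an overdose.
- Diaries, pill counts and accountability records document intake without triggering a report.

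No route requires a prompt overdose report for a one- or two-day excess without an SAE.

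**The case against.** The strongest reply is that this is a deliberate definition and no harm has been shown. Section 3.1 says that 50 mg bid lies well within the range studied in the first-in-human trial, where the drug was well tolerated. The supporting detail is redacted or sits in the Investigator's Brochure, so the three-day condition may have been reasoned. This stands in part: the documents show neither that a short excess is harmful nor why three days were chosen.

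A second reply is that an investigator could judge 900 mg in one day medically important and report it as an SAE under Section 7.4.1.1. That is plausible for the extreme case, but it rests on individual judgment. Section 6.12 was written so that reporting an overdose would not depend on seriousness.

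A third reply is that an incorrect dose may count as a major violation and so trigger immediate notice to the Sponsor, whose study team includes a Drug Safety representative (Section 6.10). Protocol 7 says major violations are defined in the Manual of Procedures, which was not available for review, and in the SAP, which does not make the link. The route may work in practice, but nothing in the two documents secures it.

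Finally, recording is not wholly absent. SAP 15 lists drug administrations with dates and reasons for dose change, and the accountability records exist. These are records, not prompt safety reports. It is also fair that a protocol amendment across about 50 sites in 10 countries is more than a change of wording if made for this point alone.

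**Conclusion.** The concern holds. Under Section 6.12 a one- or two-day overdose of any size without an SAE requires neither the overdose entry nor the expedited report. The rule expedites 675 mg over three days but not 900 mg in one day.

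The conclusion rests on reading the duration condition as applying to the whole definition, which is the natural reading of the sentence, and on the protocol and SAP alone; the Manual of Procedures could narrow the gap. The remaining gap is a known short excess above 200 mg a day that is asymptomatic or non-serious and not judged medically important. The consequence is limited to prompt safety reporting. The change is worth making because it is cheap and serves the section's own aim; there is no evidence in the documents that subjects are being harmed.

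**What to change.** In Section 6.12, remove the consecutive-days condition. Define a reportable overdose as any intake above twice the highest daily dose in a day: more than 200 mg, stated as more than 8 capsules or tablets. Counting capsules lets blinded sites apply the same rule in both arms. The recording and expedited-reporting duties can stay as they are. No new SAP listing is needed, because overdoses entered in the AE section would appear in the existing AE listings.

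The cost is one sentence, which can be included in another amendment, and a few extra reports. Ordinary slips stay below the limit: one doubled dose gives 100 + 50 = 150 mg that day, and a fully doubled day gives 200 mg, which does not exceed it.
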